Previously untreated patients (PUPs) are at particular high risk to develop high- and low-titer inhibitors. In the most recent studies (SIPPET), a 35.4% cumulative incidence of inhibitors in patients with severe hemophilia was reported within the first 50 EDs [Peyvandi et al., 2016]. In patients with inhibitors, particularly high titer, further replacement therapy with FVIII is futile and bleeds must be treated with by passing products [EMA reflection paper on ITI, 2013]. However, bypassing agents are not as effective as FVIII replacement in patients without an inhibitor [Witmer and Young, 2013]. Inhibitor eradication has been achieved with immune tolerance induction (ITI) therapy in a significant proportion of patients (approximately 70% to 85%)[Oldenburg et al., 2014]. Since patients with inhibitors have a higher disease burden and an increased mortality and morbidity compared to those without inhibitors [Witmer and Young, 2013; Walsh et al., 2015], inhibitor eradication by ITI is the gold standard of therapy.

The main goal of ITI is to restore responsiveness to FVIII treatment [Mariani et al., 2003]. ITI treatment regimens utilize ongoing, frequent, uninterrupted exposure to FVIII over a period of a few months to 2 or more years with the goal of inducing antigen-specific tolerance [DiMichele, 2007]. Multiple ITI dosing regimens have been established in different parts of the world without clear evidence of the superiority of one regimen over the other. Low-dose regimens typically utilize substitution of 50 IU/kg 3 times weekly, whereas intermediate- to high-dose regimens employ intense therapies with 100 IU/kg daily or twice daily. While these doses would lead to high FVIII levels in patients without inhibitors and, in single cases, might constitute a risk for thromboembolic events, patients with inhibitors have a marginal incremental recovery (IR) of FVIII, resulting in low or non-detectable FVIII levels in plasma during ITI therapy. To compensate for increasing FVIII activity in successful or partially successful ITI (ie, declining inhibitor titers), some physicians decrease the treatment intensity when the inhibitor titer is found to decrease and the IR of FVIII found to

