1.4 Potential Risks and Benefits

The risks include the possibility that subjects treated with rVIII-SingleChain may develop an inhibitor and that antihemophilic factors may therefore be less effective or ineffective in increasing FVIII levels and stopping or preventing bleeding. Treatment with any antihemophilic factor presents a risk of inhibitor formation particularly in PUPs in which the risk of inhibitor formation has been estimated to be up to 35.4% [SIPPET study, [Peyvandi et al., 2016](#); [Kasper, 2004](#)]. The development of an inhibitor is associated with significant morbidity and mortality, including a higher rate of bleeding complications, increased disability and a decreased quality of life [[Witmer and Young, 2013](#)]. The absolute risk of inhibitor formation with rVIII-SingleChain is currently unknown. In Study CSL627_1001 in 174 PTPs with previous exposure to > 150 EDs to FVIII products, 120 subjects achieved ≥ 50 EDs, of whom 52 subjects had ≥ 100 EDs to rVIII-SingleChain at the end of the study.

CCI [Redacted]

CCI [Redacted]

For subjects in all study arms, the potential benefits of treatment include stopping and / or preventing bleeding. In addition, rVIII-SingleChain has demonstrated an adequate safety profile for PTPs. The associated benefit-risk assessment of the study is acceptable for subjects enrolled.

Please refer to the Investigator’s Brochure for more detailed information.

2 Study Objectives and Endpoints

Overall, the study objectives in all 3 study arms are to gain additional safety information on the incidence of FVIII inhibitors (including in PUPs), frequency of adverse events (AEs), and serious AEs (SAEs) associated with the use of rVIII-SingleChain, and to gain additional information on the efficacy of rVIII-SingleChain in PTPs and PUPs with severe hemophilia A. This study will collect information on subjects undergoing surgery during the study, thereby providing information on the safety and efficacy of rVIII-SingleChain during surgery. CCI

[REDACTED]

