11.1 Sample Size Estimation

The sample size was based on the EMA guidelines for the clinical investigation of recombinant and human plasma-derived factor VIII products [EMA, 2011]. Therefore, no sample size calculations were performed. The target enrollment is at least 200 PTPs (Arms 1 and 3) completing at least 100 EDs during enrollment in all CSL-sponsored rVIII-SingleChain studies and 24 PUPs (Arm 2) completing 50 EDs of rVIII-SingleChain in this study. Thus, the study will enroll at total of least 224 subjects with severe hemophilia A.

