11.3.3.2 Primary Safety Analysis

The incidence of inhibitor formation to FVIII, based on the number of EDs and subjects specified in [Section 11.3.3.1](#) will be reported together with a (2-sided) 95% CI. However, if no inhibitor formation is observed, then the upper one-sided 97.5% confidence limit will be reported. For calculation of the incidence for each study arm, the numerator will include all subjects who develop inhibitors in each arm and the denominator will include:

- a) all PTPs with at least 100 EDs plus PTPs with less than 100 EDs but with inhibitors.
- b) all PUPs with at least 50 EDs plus PUPs with less than 50 EDs but with high-titer inhibitors.

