## 2.1 Primary Endpoint

In **Arms 1 and 3 (PTPs)**, the primary endpoint is:

- Incidence of inhibitor formation to FVIII in at least 200 PTPs with at least 100 EDs of rVIII-SingleChain.

In **Arm 2 (PUPs)** the primary endpoints are:

- Incidence of high-titer inhibitor formation to FVIII (i.e., inhibitor titer of  $\geq 5$  Bethesda units/mL during the study) in at least 50 PUPs
- Treatment success for major bleeding episodes, defined as a rating of “excellent” or “good” on the investigator’s clinical assessment of hemostatic efficacy 4-point scale.
- Annualized spontaneous bleeding rate (AsBR) during prophylaxis and on-demand treatment.

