#### The transient inhibitor incidence

- Numerators = Number of PUPs subjects who develop inhibitors and have subsequent negative results within 6 months, i.e. 183 days
- Denominators = Total number of PUPs who develop inhibitors

A two-sided 95% exact CI for the incidence of inhibitor formation will be calculated. If zero inhibitors are observed, then a one-sided 97.5% upper confidence limit will be calculated. SAS' FREQ procedure will be applied to produce an exact CI, which uses the Clopper-Pearson CI as the default method, however, Wald CIs will also be presented. The analysis will be performed also by race.

For PUPs, the incidence (with CI) of inhibitor formation to FVIII will be estimated also by Total EDs ranges. According to the Total EDs they were exposed at time of first positive FVIII inhibitor test PUPs will be classified into 0-10 EDs, >10-25 EDs, >25-50 and >50 EDs. Assessments at EDs=0 are defined as those assessments done before date and time or on the same date and time of first dose. If time of assessment or time of first dose is missing then the inhibitor result taken at the same date of the first dose will be considered as at EDs=0. An assessment done on the same date and time of a dose will be considered to be exposed to the number of EDs the subject has been exposed before that date and time. If time is missing for the assessment or the dose, then the assessment done on the same date of dose will be considered to be exposed to the EDs the subject has been exposed before the date of that dose.

Summaries of inhibitors assay test and inhibitor titer while subjects are inhibitor positive will be provided.

The incidence of inhibitor formation to FVIII will be also summarized at the assessment of 10, 50 and 100 EDs in the current study as collected in the eCRF.

Analysis will be performed overall, by region and considering the Japanese subgroup only.

CCI

CCI

CCI

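### The SAP adds a Wald interval beside the exact one for inhibitor incidence, without excepting zero or few events, where the Wald interval misleads

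*SAP*

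**What the plan says.** SAP 4.7.1 sets out the intervals in the paragraph after the transient-inhibitor definition. The lead statement is "A two-sided 95% exact CI for the incidence of inhibitor formation will be calculated". For no events the rule is "If zero inhibitors are observed, then a one-sided 97.5% upper confidence limit will be calculated". Protocol 11.3.3.2 has the same rule: "if no inhibitor formation is observed, then the upper one-sided 97.5% confidence limit will be reported". The SAP then describes the SAS procedure, "which uses the Clopper-Pearson CI as the default method, however, Wald CIs will also be presented". Nothing limits the Wald interval to tables with enough events. Beyond calling the exact method the default, nothing says which interval to interpret when the two differ.

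The protocol does not mention a Wald interval, and SAP 4.11, which lists changes from the protocol, gives no reason for adding one.

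The same SAP paragraphs repeat the analysis by race, by region, for the Japanese subgroup and, in PUPs, by four exposure-day ranges. SAP 3.5.6 suppresses tables for the subgroups defined there when they hold 3 or fewer patients.

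**The concern.** Inhibitor formation is the primary safety endpoint in both populations. The Wald interval takes its width from the observed proportion. At zero events it has no width, and at a handful of events it is too short on the upper side, which is the side that matters for a safety risk. A table that prints 0% to 0% next to an exact upper limit makes two incompatible statements of precision, and the Wald one can be read as near-certainty of no risk. The by-race, by-region, Japan and exposure-day tables cut a PUP target of 24 into cells where zero or one event is easily seen.

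**Working it through.** **Inputs from the documents**
- PTPs: n=200, the minimum in "Incidence of inhibitor formation to FVIII in at least 200 PTPs with at least 100 EDs of rVIII-SingleChain" (SAP 2.1).
- PUPs: n=24, from "24 PUPs (Arm 2) completing 50 EDs of rVIII-SingleChain in this study" (protocol 11.1).
- PUP all-titer rate: "a 35.4% cumulative incidence of inhibitors in patients with severe hemophilia was reported within the first 50 EDs" (protocol 1.1).
- Rate with this product: "The absolute risk of inhibitor formation with rVIII-SingleChain is currently unknown" (protocol 1.4). No expected PTP rate or PUP high-titer rate is given, and no sample size calculation was done, so there is no planned precision figure to reproduce.

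**Assumptions**
- PTP true rate 0.1% to 2%.
- PUP high-titer true rate 5% to 35.4%. The upper end is the all-titer figure, of which high-titer is a subset.

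**Formulas**
- Wald: p̂ ± 1.96·√(p̂(1−p̂)/n).
- Exact (Clopper-Pearson): beta quantiles. At zero events the one-sided 97.5% upper limit is 1 − 0.025^(1/n).
- Coverage at true rate p: the sum of binomial probabilities P(X=x) over every x from 0 to n whose interval contains p.

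**Step 1: zero events (no assumed rate needed).** With p̂=0, Wald is 0 ± 0. The exact upper limits are:
- 0/200: 1 − 0.025^(1/200) = 1.83%.
- 0/24: 1 − 0.025^(1/24) = 14.2%.
- 0/5, a small cell above the suppression threshold: 1 − 0.025^(1/5) = 52%.

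**Step 2: few events (no assumed rate needed).** For 1/200, p̂=0.005 and √(0.005·0.995/200)=0.00499, so the Wald half-width is 0.98 percentage points.

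| Events/n | Wald | Exact |
|---|---|---|
| 1/200 | −0.48% to 1.48% | 0.01% to 2.75% |
| 2/200 | −0.38% to 2.38% | 0.12% to 3.57% |
| 3/200 | −0.18% to 3.18% | 0.31% to 4.32% |
| 1/24 | −3.8% to 12.2% | 0.1% to 21.1% |
| 2/24 | −2.7% to 19.4% | 1.0% to 27.0% |
| 3/24 | −0.7% to 25.7% | 2.7% to 32.4% |

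The lower limit is negative for 1 to 3 events at both sizes and positive from 4 events. The Wald upper limit after one inhibitor lies below the exact upper limit after none: 1.48% against 1.83% at n=200, and 12.2% against 14.2% at n=24.

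**Step 3: coverage over the assumed rates.**

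| n | True rate | Expected events | Wald | Exact |
|---|---|---|---|---|
| 200 | 0.1% | 0.2 | 18.1% | 98.3% |
| 200 | 0.25% | 0.5 | 39.4% | 98.6% |
| 200 | 0.5% | 1 | 63.3% | 98.1% |
| 200 | 1% | 2 | 86.5% | 98.4% |
| 200 | 1.5% | 3 | 80.0% | 98.9% |
| 200 | 2% | 4 | 90.8% | 96.2% |
| 24 | 5% | 1.2 | 70.7% | 99.4% |
| 24 | 10% | 2.4 | 91.3% | 99.3% |
| 24 | 15% | 3.6 | 88.8% | 96.0% |
| 24 | 20% | 4.8 | 87.3% | 98.3% |
| 24 | 25% | 6 | 93.9% | 97.0% |
| 24 | 35.4% | 8.5 | 94.3% | 97.0% |

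Wald coverage moves in a saw-tooth between these rates. On a fine grid from 0.1% to 2% at n=200 it peaks at 94.5% (true rate 1.47%) and averages 76%.

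**Step 4: small cells.** Even at 35.4%, Wald coverage is 81% at n=4 and 83% at n=5.

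**Step 5: the alternative.** Wilson intervals have width at zero events (0/200: 0% to 1.88%). They cover 91% to 98% at the six PTP rates, and 97.0% at n=24 with a rate of 35.4%.

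**The case against.** - **The exact interval leads.** It is the default, and zero events has its own rule in both documents, so the 0% to 0% case always has a valid limit beside it. This stands, and it makes the flaw one of presentation. It does not make the second interval correct.
- **No expected count is stated.** A reader might infer that the trial expects counts at which Wald fails. The documents do not support that, because they give neither a PTP rate nor a high-titer rate. The coverage figures are conditional on assumed rates; Steps 1 and 2 are not.
- **Wald is adequate for PUPs at the protocol's own rate.** A reader might infer that 24 PUPs is simply too few for Wald. At 35.4% its coverage is 94.3%, so that reading fails for all-titer incidence. A larger shortfall needs a lower rate, as may apply to high-titer inhibitors, or a smaller cell.
- **The PTP report is done.** The SAP's list of changes dates it to November 2019. This stands. What remains is the PUP tables and any PTP tables repeated in the final complete report that SAP 1 describes.
- **Very small subgroups are suppressed.** This is true at 3 or fewer patients, but cells of 4 or 5 are still printed. The exposure-day ranges are not among the subgroups listed in SAP 3.5.6, so it is unclear whether the rule reaches them.
- **Nothing is decided on the interval.** No p values are planned, and the incidence analysis has no success threshold. This also stands and limits the severity.

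**Conclusion.** The concern holds in limited form. The SAP plans a supplementary interval that is uninformative at zero events, has an impossible lower limit at 1 to 3 events (n=200 or 24), and understates the upper limit at low counts. Those facts need no assumed rate. Coverage well below 95% follows only under assumptions: 18% to 91% at the six PTP rates tabulated, and 71% to 94% at the PUP rates tabulated, with a negligible shortfall at 35.4%. The places affected are the PUP high-titer endpoint, the race, region, Japan and exposure-day cells with more than 3 patients, and any PTP tables produced again.

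It would be wrong to conclude that the primary safety endpoint lacks a valid interval, since the exact one is always planned. Severity is minor.

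**What to change.** In SAP 4.7.1, delete the clause that adds Wald intervals and state that the exact Clopper-Pearson interval, with the one-sided limit at zero events, is the one to interpret. If a less conservative companion is wanted, use the Wilson score interval.

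The cost is one SAP sentence and one option in the SAS code. The small downside is that any PTP tables repeated in the final report may differ in format from those in the 2019 PTP report; a footnote can explain this.

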#### 4.7.2 Adverse Events

An AE is any untoward medical occurrence in a subject or clinical investigation subject administered a pharmaceutical product and which does not necessarily have a causal relationship with this treatment.

Adverse events will be coded and grouped by SOC and PT using the MedDRA Version 16.1 or higher.

An AE will be regarded as treatment-emergent (TEAE) if it was present prior to the first dose of rVIII-SingleChain and subsequently worsened in severity, or was not present prior to the first dose but subsequently appeared. For this determination, partially missing dates will be handled as outlined in [4.12.1](#). An AE will be assumed to be treatment-emergent if non-treatment emergence cannot be reasonably ruled out. All AEs reported for PTP in Arm 1 will be considered treatment-emergent.

TEAEs will include AEs that occurred during the surgical period, but will exclude TEAEs during the CCI period. A summary table with all the TEAEs that occurred during the study will be also provided.

Summary of AEs while subjects are inhibitor positive should be performed. All AEs while subjects are inhibitor positive will be listed. Serious AEs while subjects are inhibitor positive will also be listed.

An overview summary table of COVID-19 associated treatment-emergent adverse events (TEAEs), including number and percentages of subjects as well as the number of events, will be provided if the number of Covid-19 associated TEAE is at least equal to 10. Otherwise, Covid-19 associated TEAEs will only be listed.

TEAEs with missing causality assessment will be considered as related.

TEAEs leading to withdrawal are all TEAEs reported on the AE log with “Was subject terminated from study due to the AE” as “Yes” or “Action taken with study drug” with response of “Permanently discontinued”.

The following will be summarized by SOC and PT; displaying the number and percentage of subjects who experience at least 1 event, as well as the total number of events:

- All AEs. This will include TEAEs, and AEs that are not treatment emergent.
- All SAEs. This will include TE SAEs, and SAEs that are not treatment-emergent.
- TEAEs
- Related TEAEs
- Non-serious TEAEs
- Non-serious TEAE by frequency threshold of preferred term (>1%, >2%, >3%, >4%, and >5% in either age cohort)
- TE SAEs

- Related TE SAEs
- TEAEs by maximum severity. If a subject experiences multiple events that map to a single PT, the only the most severe event will be counted.
- Covid-19 TEAEs (considering the same rule of 10 AEs described for the summary table)
- TEAEs while subjects are inhibitor positive

In addition, the SOCs and PTs will be displayed in decreasing frequency. These displays will include the number of subjects who experience at least 1 event, as well as the total number of events.

TEAEs and TE SAEs will be summarized for the Safety population. TEAEs starting during the surgical period will be summarized by SOCs and PTs for the Surgery population. TEAEs starting during the **CCI** period will be summarized overall and by SOCs and PTs for the **CCI** population.

All AEs (including all SAEs) will be presented in the individual subject listings. SAEs, deaths, and discontinuations due to AEs will be supported by separate listings.

AEs occurring within one month prior to positive inhibitor development will be listed.

#### 4.7.2.1 Treatment-emergent Adverse Events of Special Interest

Treatment-emergent AEs of special interest (AESIs) will be summarized by category and PT; displaying the number and percentage of subjects who experience at least one event, as well as the total number of events. The treatment-emergent AESIs and how they will be identified are outlined below:

- Thromboembolic Events (TEE) - Standardised MedDRA Queries (SMQ) TEE (narrow)
- Hypersensitivity - SMQ hypersensitivity (narrow)
- Anaphylactic reactions - SMQ Anaphylactic reaction (narrow).

**Note:** In addition to the SMQ search, a medical review of the AEs may be performed to determine which AESI are confirmed cases.

Treatment-emergent AESIs will be summarized for the Safety population.

Separate listings of AESI data will be also provided: subject, SOC, PT, reported term, causality, seriousness, start and end date/time of events will be displayed.

#### 4.7.2.2 Medical events of special interest

Medical events of special interest include:

- Minor surgery
- Hospital admission for less than 24 hours for events not considered as SAEs
- Positive test result for inhibitors performed at local laboratory
- Overdose
- Hypersensitivity reactions
- Thrombotic events

The number and percentage of subjects with any medical events of special interest, as well as the total number of events, will be presented.

The medical events of special interest will be summarized by category and sub-category; displaying the number and percentage of subjects who experience at least one event, as well as the total number of events (analogous to the AE display by SOC and PT).

Medical events of special interest will be summarized by inhibitor status and on overall for the Safety population.

#### **4.7.3 Local tolerability**

Local tolerability will be summarized for the Safety population. Assessments during the [REDACTED] period will be excluded from the summary on the Safety Population and presented separately for the [REDACTED] population.

##### **4.7.3.1 Subject Assessments**

In all 3 Arms, subjects' overall perception of local injection site reactions after each injection will be rated as: None (0), Very slight (1), Slight (2), Moderate (3), and Severe (4). The number and percentage of subjects with at least 1 assessment and the total number of assessments will be summarized.

The number and percentage of subjects with each rating and the number and percentage of events with each rating will be summarized. A reaction will be defined as a rating of very slight, slight, moderate, or severe. The number and percentage of subjects with any reaction, and the total number of reactions will be presented.

##### **4.7.3.2 Investigator Assessments:**

###### Erythema

In Arm 2 and Arm 3, investigators will assess local tolerability after each injection. These will be rated as follows: None (0), Very slight (barely perceptible) (1), Well-defined (2), Moderate to severe (3), Severe (beet redness) to slight eschar formations (injuries in depth) (4). The number and percentage of subjects with at least 1 assessment and the total number of assessments will be summarized. The number and percentage of subjects for each rating and the number and percentage of events for each rating will be summarized.

###### Itching, pain and heat

For itching, pain and heat, the number and percentage of subjects with each severity and the number of events with each severity will be presented.

###### Edema or induration

The size of any edema or induration will be determined by measuring the smallest and largest diameters. For the smallest and largest size of edema or induration, the maximum size across all assessments will be summarized using descriptive statistics.

A separate analysis will be produced on overall investigator assessments while subjects are inhibitor positive on PUPs.

#### **4.7.4 Laboratory findings**

Laboratory safety parameters will be measured at the following timepoints:

- For PUPs assigned to Prophylaxis regimen: during Screening, every month until 25 EDs, and every 3 months after 25 EDs and/or End-of-Study Visit.
- For PUPs assigned to On-Demand regimen: during Screening, during Follow-up visits 1 month after each rVIII-SingleChain dose and/or End-of-Study Visit.
- For PTPs: during screening, every 3 months until the subject reaches 50 EDs, and then yearly until End-of-Study Visit as detailed in the Schedule of Assessment in the Clinical Study Protocol (CSP) Amendment 3 dated 27 January 2017.
- CCI [REDACTED]

Laboratory results (hematology and biochemistry) along with the change from baseline will be summarized by parameter and study visit. CCI [REDACTED]

[REDACTED] Baseline is the last non-missing result prior to the first infusion in the current study. Only scheduled visits will be displayed. The change from baseline to the smallest value after first dose of study product, largest value after first dose of study product, and final value will also be summarized. All visits (including unscheduled, pre/post-surgery visits, CCI [REDACTED]) will be included in the determination of these maximum/minimum changes from baseline. The number and percentage of subjects with treatment-emergent abnormal hematology and biochemistry values (baseline value normal and post-baseline value abnormal) as assessed by the investigator and recorded on the database as Clinically Significant (CS) will be tabulated by scheduled visit, as well overall. A subject will be counted as having a CS abnormal result as overall result the subject has at least one clinically significant abnormal result after baseline, including unscheduled visits. Laboratory values will be converted to the standard units and this will be documented in the study data tabulation model (SDTM) documentation.

Laboratory results will be provided in the Safety population and presented overall and subgroups based on age in this study. For PTPs: 0 to < 6 years, ≥ 6 to < 12 years, ≥ 12 to < 18 years and ≥ 18 to ≤ 65 years, 0 to <12 years, ≥12 to ≤ 65 years.

